### 3.2. Protocol Deviations

Protocol deviations are defined as a deviation from the approved protocol.

Prior to database lock, NeRRe will be responsible for producing the final protocol violation file (formatted as a Microsoft Excel file), in collaboration with the data monitoring group; this file will include a description of the protocol violation and the categorization as minor/major, relevant / not relevant. Deviations classified as relevant will result in exclusion of the subject from the Per Protocol Population. This file will be finalized and signed prior to hard database lock, after the blinded data review meeting (BDRM).

In addition, the following protocol deviations will be programmatically derived by Cytel:

- 1) Category = Non-compliance with diary completion
  - PD Reference 3.9: Less than 70% compliance with hot flush diary completion at Baseline (Visit 3).
  - PD Reference 3.10: Less than 70% compliance with hot flush diary completion at Week 4 (Visit 5).
  - PD Reference 3.11: Less than 70% compliance with hot flush diary completion at Week 12 (Visit 7).
  - PD Reference 3.12: Less than 70% compliance with hot flush diary completion at Week 2 (Visit 4), Week 8 (Visit 6) or Week 16 (Visit 8).

Compliance will be calculated for Baseline, Week 2, Week 4, Week 8, Week 12 and Week 16, using the same 7 days (or less than 7 days if this is the case per the rules defined in section 4.3.2) used in the analysis of HF frequency & severity.

The 70% cut-off essentially means that at least 10 of the 14 possible diary entries will need to have been completed for the subject to be in the PP population.

2) Category = Non-compliance with study medication

PD Reference 4.2: Subject <80% compliant with once-daily dosing of IMP.

IMP compliance will be based on the number of capsules taken (section 4.8.1). The compliance calculation should be across the whole 12-week double-blind treatment period (not visit specific). IMP should not be missing.

Relevant protocol deviations will be summarised by treatment group for the Randomised Analysis Set. All protocol violations will be presented in the data listings.

## **4. STATISTICAL METHODS**

### **4.1. Sample Size Justification**

The total sample size for the trial yields high power for the expected large difference from placebo in hot flush reduction from baseline and adequate power for moderate difference.

Assuming a common standard deviation (SD) of 4.4, N=27 per treatment group has ~95% power ( $\alpha=0.05$  2-sided) via trend test across all doses including placebo if the true underlying dose response is non-decreasing from a reduction of 4 moderate or severe hot flushes per day on placebo up to 8 on the highest dose of NT-814. N=33 per treatment group is required for 95% power for pairwise comparison of the highest dose to placebo under these same assumptions. Hence, a total of 150 completed subjects (30 x 5) was used for the simulations of adaptive design. [Note, the actual performance / power for the adaptive designs may be higher than the values cited in this report since additional subjects will be added to selected dose groups to better inform on safety.] The actual sample size is determined by the adaptive dose-finding design algorithm (See Appendix B from the protocol). In addition, the actual sample size is increased by 10% to allow for subjects who withdraw prematurely and so the initial sample size is 165 subjects.

The interim reviews will also include a review of the estimates used in defining the starting sample size. If the observed variance or delta are lower than the original estimates the sample size for the dose groups that are continuing to be evaluated may be increased. For this reason, the protocol permits a total of up to 300 subjects to be randomised into the study.

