PLANNED SAMPLE SIZE	
For the efficacy objectives of the study, assuming a common standard deviation (SD) of 4.4, N=27 per treatment group has ~95% power (alpha=0.05 2-sided) via trend test across all doses including placebo if the true underlying dose response is non-decreasing from a reduction of 4 hot flushes on placebo up to 8 on the highest dose of NT-814. N=33 per treatment group is required for 95% power for pairwise comparison of the highest dose to placebo under these same assumptions. Hence, a total of 150 completed subjects (30 x 5) was used for the simulations of adaptive design. The actual sample size will be determined by the adaptive dose-finding design algorithm outcomes. In addition, the initial actual sample size is increased by 10% to allow for subjects who withdraw prematurely and so the initial sample size will be 165 subjects.
 
The sample size allows for 95% power since each of the four co-primary endpoints are required to demonstrate statistical significance to yield a firm conclusion of beneficial treatment effect on hot flushes. Conservatively, assuming independence among the four endpoints, this would yield approximately 81% power overall for achieving statistical significance for each of
										

 Subjects who have not had a mammogram within the guidelines may have one performed as part of the screening process

	
the four endpoints. Thus, overall power for the trial is estimated to be at least 81%; the actual power depends on the unknown magnitudes of correlations among the co-primary endpoints.

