### **7. SELECTION AND WITHDRAWAL OF SUBJECTS**

#### **7.1 Subject numbers**

Participants in the clinical investigation are referred to as “subjects”.

The initial estimated sample size for the study is 165 subjects. However, the total number of subjects may be higher or lower according to the outcome of the interim analyses (see Section 11).

The maximum number of subjects randomised into the study will be 300.

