### 8.6.1 Justification for Study Design

The study is a dose-range finding study, with assessment of dose-response based on both efficacy and safety. A four-fold range of doses will be evaluated which broadly encompasses the equivalent exposures to those evaluated in the RELENT-1 study that were associated with efficacy (See Section 5.1.3).

The study will have an adaptive design component in which the number of subjects randomised to each treatment group is modified on the basis of emerging safety and efficacy data. This design enables a broad range of doses to be evaluated in the first instance, but with the ability to reduce the number of doses of NT-814 being evaluated if this emerging data shows that there is no advantage in continuing to evaluate them. The interim reviews also enable the sample size (per treatment group) to be assessed on an ongoing basis and to be increased if the estimates of treatment effect and variability used to derive the sample size originally prove to be incorrect. These adaptive features ensure that the study has the greatest probability of success while making efficient use of the trial population.

The study will be placebo controlled to minimise assessment bias. Placebo is considered an acceptable reference group for studies in PM VMS as the disorder, whilst uncomfortable and disruptive to the affected individual, is not life-threatening or limiting, and studies are typically of limited duration. Experience from multiple studies in women with VMS has shown that a placebo response of up to 60% can be expected and so even subjects allocated to placebo should expect to receive some benefit from study participation. The use of placebo is also recommended by both the United States FDA and EU CHMP disease-specific guidelines.

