## 11.2 Interim Reviews

A number of interim analyses (IA) are planned to enable the following two questions to be addressed as the trial progresses:

- 1) Do the emerging efficacy and safety data support the continued evaluation of all four NT-814 doses?
- 2) Do the assumptions used in the original sample size estimate remain valid?

The first IA will be conducted after efficacy data for the frequency and severity of hot flushes is collected through Week 4 from 30 patients randomized in equal proportions to the four NT-814 doses and placebo. The DRC will review the HF frequency and severity results, together with all available safety data, and will determine the randomisation ratios for subjects subsequent enrolled into the study. The ratio may be changed to optimise the adaptive design to estimate doses with target levels of weekly average daily HF reduction from baseline of between 6 and 8. The adaptive design algorithm will be based on Bayesian Emax dose-response modeling and / or T-statistic adaptive dose-finding design. The DRC will have dose assignment recommendations by each of those adaptive dose-finding algorithms and assign the randomization ratio that best integrates the safety and efficacy objectives of the trial and the adaptive design results. Additional details regarding the adaptive algorithms and their performance characteristics are in the adaptive dose-finding design simulation report (Appendix B). Subsequent IA's will be conducted similarly, after Week 4 data from each cohort of ~30 additional subjects become available. The DRC will evaluate stopping criteria according to the IA algorithms as described in Appendix B and decide on stopping assignment of subjects to specific doses or stopping the trial for an efficacy or safety conclusion, and dose choice for subsequent study or futility.

The DRC will be unblinded to treatment allocation. Subjects will continue to be recruited and randomised while the interim analyses are being undertaken.

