**METHODS**

First, in order to arrive at some example TRUE underlying dose-response scenarios, prior data on hot flush reduction was examined. NT-814 has shown efficacy in reduction of hot flushes over a 2-week period in a Phase 1/2a trial. Mean reductions in hot flush frequency of up to 9 per day from a baseline frequency ~10-12 were observed (with an observed SD of change from baseline ranged between ~3.4 to ~4.9; SD back-calculated from SE's from the analysis model yielded SD's of change ~3.7). In order to obtain longer term prior data to inform on expected variability, the Duavee label was also examined. It yielded SD's of change ~4.4 after 4 weeks' treatment and ~3.6 after 12 weeks' treatment. Based on these prior data, an SD=4.4 and somewhat conservative magnitudes of treatment effect were used to simulate adaptive design outcomes and performance characteristics. The following TRUE underlying dose-response curves were examined:

label	Assumed TRUE underlying mean hot flush frequency reduction from baseline (SD=4)				
	placebo (dose0)	dose1	dose2	dose3	dose4
DRCID 1	4	4	5	6	7
DRCID 2	4	5	6	7	8
DRCID 3	4	5	6	8	8
DRCID 4	4	6	8	8	8

The total sample size for the trial yields high power for the expected large difference from placebo in hot flush reduction from baseline and adequate power for moderate difference.

Assuming a common standard deviation (SD) of 4.4, N=27 per treatment group has ~95% power ( $\alpha=0.05$  2-sided) via trend test across all doses including placebo if the true underlying dose response is non-decreasing from a reduction of 4 hot flushes on placebo up to 8 on the highest dose of NT-814. N=33 per treatment group is required for 95% power for pairwise comparison of the highest dose to placebo under these same assumptions. Hence, a total of 150 completed subjects (30 x 5) was used for the simulations of adaptive design. [Note, the actual performance / power for the adaptive designs may be higher than the values cited in this report since additional subjects will be added to selected dose groups to better inform on safety.] The actual sample size will be determined by the adaptive dose-finding design algorithm.

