### **4.2. General Statistical Methods and Data Handling**

#### **4.2.1. General Methods**

Tabulations will be produced for appropriate demographic, baseline, efficacy and safety parameters. For categorical variables, summary tabulations of the number and percentage within each category of the parameter will be presented. Percentages will be calculated based on the number of non-missing values, except if indicated differently. In case of counts equal to zero, reporting will be presented as 0 (with no percentage). For continuous variables, the mean, median, standard deviation, minimum and maximum values will be presented.

For specific categorical efficacy parameters, two-sided 95% confidence interval might be presented.

Formal statistical hypothesis testing will be performed on the primary and secondary efficacy endpoints with all tests conducted at the 2-sided, 0.05 level of significance. Summary statistics will be presented, as well as confidence intervals on selected parameters, as described in the sections below. P-values will be reported with 4 decimals places.

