## **5. CHANGES TO PLANNED ANALYSES**

As of this date, there have been no changes between the protocol-defined statistical analyses and those presented in this statistical plan.

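### SAP 4.1 has the variance condition for increasing the sample size the wrong way round: a higher observed variance, not a lower one, calls for more subjects

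*SAP*

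**What the plan says.** SAP 4.1 plans on a common SD of 4.4 and a reduction of 4 moderate or severe hot flushes per day on placebo against 8 on the highest dose. It then says the interim reviews will revisit these planning estimates: "If the observed variance or delta are lower than the original estimates the sample size for the dose groups" still being evaluated may be increased. It gives this as the reason the protocol allows up to 300 randomised subjects.

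The protocol covers the same adaptation without giving a direction:

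- Section 8.6.1 allows the size per group "to be increased if the estimates of treatment effect and variability used to derive the sample size originally prove to be incorrect".
- Section 7.1 says that "the total number of subjects may be higher or lower according to the outcome of the interim analyses".
- Section 11.2 makes this one of the two questions for the interim analyses: "Do the assumptions used in the original sample size estimate remain valid".

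SAP section 5 states that "there have been no changes between the protocol-defined statistical analyses and those presented in this statistical plan", so the SAP does not present itself as narrowing the protocol.

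**The concern.** The SAP sentence ties two quantities to one word, lower, although they act on sample size in opposite directions. It is right for delta and reversed for variance. It names the variance case in which the trial has more power than planned as a ground for adding subjects, and omits the case in which the trial has less.

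The Data Review Committee (DRC) sees unblinded data and has discretion over the sample size. The written condition is therefore what a later reader would use to judge whether an increase was planned. On the SAP's wording, an increase after a high observed variance, which would be justified, has no support in the SAP, while one after a low observed variance does.

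**Working it through.** **Inputs**

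- Two-sided alpha 0.05: SAP 4.2.1 ("all tests conducted at the 2-sided, 0.05 level of significance") and the protocol's sample-size text.
- Delta = 8 − 4 = 4 per day, highest dose against placebo; planning SD 4.4 (SAP 4.1, Protocol 11.1.1).
- 30 completers per arm, 150 in total, plus 10% for withdrawals (same sections).
- SDs from prior data in the Methods of Protocol Appendix B. The earlier two-week trial is described "with an observed SD of change from baseline ranged between ~3.4 to ~4.9", with about 3.7 back-calculated from its analysis model. A product label gave about 4.4 at 4 weeks and about 3.6 at 12 weeks.

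**Reproducing the plan's own figure**

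Normal approximation: n per arm = 2 × [SD × (z₀.₉₇₅ + z₀.₉₅) / delta]² = 2 × [4.4 × (1.960 + 1.645) / 4]² = 31.4, so 32. The exact two-sample t-test (noncentral t) gives 94.7% power at 32 and 95.3% at 33. That matches the stated 33 per group for 95% pairwise power.

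**Direction**

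n is proportional to SD²/delta². With delta fixed, n moves with the variance. From the planned variance of 4.4² = 19.36:

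- SD 3.4: (3.4/4.4)² = 0.60, so about 40% fewer subjects.
- SD 4.9: (4.9/4.4)² = 1.24, so about 24% more.

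**Power and size over the reported SDs** (exact t, delta 4)

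| Observed SD | Power at 30/arm | n/arm for 95% | SAP 4.1 as worded |
|---|---|---|---|
| 3.4 | 99.4% | 20 | may increase |
| 3.6 | 98.8% | 23 | may increase |
| 3.7 | 98.4% | 24 | may increase |
| 4.4 (plan) | 93.3% | 33 | – |
| 4.9 | 87.5% | 40 | no mention |

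In each row below the planned SD, 30 per arm already exceeds what 95% power needs. At SD 4.9 it falls 10 per arm short. Meeting that need takes 40 × 5 = 200 completers, or 200 × 1.1 = 220 randomised by the plan's own 10% convention, which is inside the 300 maximum.

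**Delta, for comparison** (SD 4.4, 30 per arm; these deltas are assumed)

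- Delta 3.5: 85.8% power, 43 per arm for 95%.
- Delta 3.0: 73.8% power, 57 per arm for 95%.

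A lower delta does need more subjects, so that half of the sentence stands.

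**Whether the direction is given elsewhere**

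It is not. The three protocol sections quoted above are neutral. The stopping guidance in Appendix B and the interim procedures in SAP 4.3 deal with dose allocation and stopping, not with re-estimating sample size from the observed variance.

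**The case against.** The strongest case on the other side concerns weight, since the reversal itself is plain.

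1. **Probably a drafting slip, and permissive.** The sentence has no threshold or formula and says only that the size may be increased. Protocol 8.6.1 already allows an increase if the variability estimate proves wrong, and Protocol 11.1.2 foresees adding subjects to assess safety. So the wording forbids nothing and forces nothing. This stands, and it limits the consequence. It does not make the sentence right.

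2. **Timing.** SAP 3.1 says the list of deviations for the per-protocol set has already been finalised at the blinded data review, and SAP 4.6.2.7 reports what was seen at that meeting. This version therefore appears to post-date the blinded review, when recruitment decisions were very likely over. This also stands, and it makes a record of what was done the main useful action now. Whether the DRC worked from this wording cannot be known, because its Charter is not among the documents.

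3. **Selective figures.** SD 4.9 is the top of the range from a two-week trial, and 4.4 was a cautious choice against the other values. Pairwise power is already 93.3% at the planned SD with 30 per arm, so the loss at SD 4.9 runs from 93.3% to 87.5%, not from 95%. The plan also cites a trend test: "N=27 per treatment group has ~95% power (alpha=0.05 2-sided) via trend test". For a linear contrast on means 4, 5, 6, 7, 8 with 30 per arm, power is about 97% at SD 4.4 and 94% at SD 4.9. These points are fair on size. Pairwise comparison with placebo is, however, the SAP's main analysis, and the direction is the same on either test.

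**Conclusion.** The concern holds. The variance half of the SAP 4.1 condition is reversed, the delta half is correct, and neither document states the variance direction correctly anywhere else. Over the SDs the protocol itself reports, the wording supports adding subjects where pairwise power is 98% to 99%, and is silent where it is 87.5% and 40 per arm would be needed.

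These figures assume fixed equal arms, a true delta of 4, frequency as the endpoint, and no baseline adjustment. Adaptive allocation and the repeated-measures model will shift the values, but not the direction.

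The consequence is limited. The starting size of 165 and the planned analyses are unaffected, and the protocol is not contradicted. It should be corrected because it is the SAP's stated ground for going up to 300 subjects.

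**What to change.** In SAP 4.1, change the condition so that the size of the continuing dose groups may be increased when the observed variance is **higher**, or the observed delta is **lower**, than the planning value, up to the maximum of 300 randomised. Check the sentence against Protocol 8.6.1, and correct the DRC Charter if it carries the same wording.

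If the interim reviews have already taken place, state in the CSR how the observed variance was compared with the planning value and in which direction it was applied to any change in sample size.

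The cost is one sentence in the SAP, possibly one in the Charter, and one statement in the CSR. The starting sample size and the final analyses do not change.

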### **4.2. General Statistical Methods and Data Handling**

#### **4.2.1. General Methods**

Tabulations will be produced for appropriate demographic, baseline, efficacy and safety parameters. For categorical variables, summary tabulations of the number and percentage within each category of the parameter will be presented. Percentages will be calculated based on the number of non-missing values, except if indicated differently. In case of counts equal to zero, reporting will be presented as 0 (with no percentage). For continuous variables, the mean, median, standard deviation, minimum and maximum values will be presented.

For specific categorical efficacy parameters, two-sided 95% confidence interval might be presented.

Formal statistical hypothesis testing will be performed on the primary and secondary efficacy endpoints with all tests conducted at the 2-sided, 0.05 level of significance. Summary statistics will be presented, as well as confidence intervals on selected parameters, as described in the sections below. P-values will be reported with 4 decimals places.

#### **4.2.2. Computing Environment**

All descriptive statistical analyses will be performed using SAS statistical software (Version 9.4), unless otherwise noted. Medical History and adverse events will be coding using the Medical Dictionary for Regulatory Activities (MedDRA) dictionary Version 21.1 or in the latest version available prior to DBL. Concomitant medications will be coded using World Health Organization (WHO) Drug Version Sep2018 B3 Global or the latest version available prior to DBL.

#### 4.2.3. Adjustments for Covariates

All efficacy endpoints will be analysed by statistical models including treatment, score/endpoint at baseline, randomisation stratification factor (region: North America / Europe) as fixed effect covariates.

#### 4.2.4. Multiple Comparisons/Multiplicity

No adjustment for multiple comparisons will be used for this Phase 2 study.

#### 4.2.5. Subpopulations

The descriptive analysis of the co-primary endpoints analysis will be repeated by region (North America or Europe).

#### 4.2.6. Withdrawals, Dropouts, Loss to Follow-up

Subjects who withdrew from the study after randomisation will not be replaced.

#### 4.2.7. Missing, Unused, and Spurious Data

In general, there will be no substitutions made to accommodate missing data points. All data recorded on the CRF will be included in data listings that will accompany the clinical study report.

Sensitivity analyses may be performed, and are detailed in the corresponding efficacy endpoint sections.

Clinical laboratory values as “<X” where X is the numerical value of the limit of quantification (LOQ) established by the laboratory will be imputed by LOQ/2 for summaries in the tables.

Clinical laboratory values as “>X” where X is the numerical value of the limit of quantification (LOQ) established by the laboratory will be imputed by LOQ for summaries in the tables.

#### 4.2.8. Study Day

Study Day is the number of days since the date of the administration of the first dose of randomised study treatment (Study Day 1). If the assessment date is after the date of the first dose, the study day is calculated as (date of assessment - date of the first randomised treatment intake date+ 1). If the assessment date is prior to the date of the first dose, the study day is calculated as (date of assessment - date of the first randomised treatment intake date). All assessments prior to Study Day 1, including the Screening visits 1 and 2, will have negative study days (i.e. no Day 0).

